4.1.1 Study Drug Administration Timing

In consideration of the latest time point of treatment application before graft reperfusion (ie. beginning of renal vein anastomosis), study treatments will be administered preoperatively at any one point in time, from time of admission up to the beginning of renal vein anastomosis **before graft** reperfusion. Due to the biologic half-life of C1INH (approximately 2.5 to 3.8 days), the time difference between early and late intraoperative treatment application, is thought to be negligible. In addition, the patients will receive study treatments at 24 hrs. post-transplant. This will constitute the entirety of C1INH vs. placebo administration. The study format is shown below in figure 3.

[figure not shown]

Figure 3: Study format to evaluate C1INH in DGF.

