4.6.2 Safety Variables

4.6.2.1 Adverse Drug Reactions: The most serious adverse reaction reported in subjects in clinical studies who received Berinert® was an increase in the severity of pain associated with hereditary angioedema. In a placebo controlled clinical study, the incidence of adverse events occurring in more than 4% of subjects (n = 43) receiving Berinert® up to 72 hours after infusion was nausea (7%), headache (7%), abdominal pain (7%), dysqeusia (4.7%), vomiting (2.3%), pain (2.3%), and muscle spasms (2.3%). Adverse reactions can persist 7-9 days after infusion and have been reported to be abdominal pain (6.5%), diarrhea (4.6%), nausea (6.5%), vomiting (4.6%), headache (11.1%), hereditary angioedema recurrence (11.1%), muscle spasm (5.6%), and pain (5.6%). Subjects were tested at baseline and after 3 months for exposure to parvovirus B19, HBV, HCV, and HIV-1 and HIV-2. No subject who underwent testing evidenced seroconversion or treatment-emergent positive polymerase chain reaction testing for the above pathogens. Post-marketing reports from Europe since 1979 in patients receiving Berinert®

for treatment of HAE include hypersensitivity/anaphylactic reactions, a few suspected cases of viral transmission, including cases of acute hepatitis C, injection-site pain, injection-site redness, chills, and fever. See Novation Drug Monograph for Berinert® (Appendix B).

- 4.6.2.2 Assessment of Risk for Thrombotic Events with C1INH Administration: Patients with known risk factors for thrombotic events will be monitored for signs and symptoms of thrombosis, such as new onset swelling and pain in the limbs or abdomen, new onset chest pain, shortness of breath, loss of sensation or motor power, or altered consciousness, vision, or speech. To address the increased risk of TE, we will apply the Well's criteria for diagnosis of DVT (http://www.mdcalc.com/wells-criteria-for-dvt) (Wells, 2003,2006,2006). Patients will be assessed with each infusion for evidence of DVT or other TEs. Those receiving a high-risk score will have lower-extremity Doppler venous ultrasounds to rule-out the presence of DVTs. In addition, routine measurements of coagulation factors to evaluate DIC (D-Dimers, fibrinogen, PT, PTT) will be performed (See Appendix A).

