4.6.3.3 Day 1-7 Assessments measured daily through day 7 or until discharge

- Berinert vs. Placebo infusion (24hrs post-transplant)
- C1 inhibitor, C3, C4 levels (prior to second dose of C1INH or placebo)
- Urine output between hours of 16-24, 40-48 post transplant
- Concomitant medications
- Serum creatinine measurements daily through Day 7 or until discharge.
- Dialysis assessment
- Vital Signs
- Clinical Assessment
- Calculated Creatinine / Calculated GFR
- Urine output measurement
- Adverse event assessment
- Hematology & chemistry profile
- PT, PTT and INR (day 1 and day 7 only)

•

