4.6.4.1 Physical Examination

A complete physical examination will include; body weight and the examination of the following body systems: general appearance, skin, HEENT (head, ears, eyes, nose, throat), cardiovascular, pulmonary, abdomen, neurological, lymph nodes, spine and extremities (skeletal). In addition, Wells Criteria Assessment will be done for presence of DVTs.

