4.6.4.8 PT, PTT and INR Tests

PT, PTT and INR tests will be performed per institutional SOC.

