4.6.4.9 Hematology and Chemistry Profile

Hematology and Chemistry profile performed per institutional SOC and will include measurements of WBC, RBC, platelets, electrolytes, BUN, glucose, T Bili, Alb, Alk Phos, AST, ALT, BUN and Albumin.

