Appendix A

Study visit										
	Screening	Transplant Day 0 (Infusion #1 C1INH vs Placebo)	Day 1±6 hrs (Infusion #2 C1INH vs Placebo)	Day 2±6 hrs	Day 3±6 hrs	Day 4±6 hrs	Day 5±1 days	Day 6±2 days	Day 7±3 days *	Day 14 ±3 days
Informed Consent	Х									
Inclusion/exclusi on criteria review	^ X									
Medical History	X									
Complete Physical Exam (Including DVT Exam) (1)	X	X	X	X	Х	X	X	X	x	
Vital										
signs/weight	Χ	Х	X	Х	Х	Х	Х	Х	Х	Х
12-lead ECG (w/in 6M)	Х									
Chest X-ray (w/in 6M)	Х									
Safety laboratory tests (CBC, CMP)	X	Х	Х	Х	х	Х	Х	Х	Х	Х
PT, PTT, D. Dimer, Fibrinogen	Х	Х	Х						Х	
Review Historical Serologies for HIV, HBV, HCV, CMV and EBV	X									
Pregnancy test (for WOCP)	X									
Urinalysis	Х									Х
Urine Output		v	v	V	V	Х	V	Х		
Measurement Estimated GFR (using MRDR or Cockroft & Gault		X	X	X	X		X		X	
equation)			Х	Х	Х	Х	Χ	Х	Х	Χ

OOMITEDENTIA		OTTIVII (DCI	ernerco, in	1 Deady	±11 1(±0	11101 11	amopia			
Allograft biopsy		Х								
Dialysis	1		+	+						
Assessment	ı	X	X	Х	Х	Х	Х	Χ	х	Х
Assessment for					1					
DVT (Using Wells	ı									
Criteria Score)	ı									
(2)		X	Х						Х	
Pneumococcal	ı									
Vaccine &	ı									
Neiserria	ı									
Menigitides	Х				 				 	 
Berinert® vs	ı									
Placebo Infusion	ı									
_		X	Х		 	 	 	  '	 	1
C3, C4 Levels		Χ	Х		 	 		'	Х	
C1 Inhibitor				T						
Level (Prior to	1									
each infusion)		Χ	X						Х	
Campath or	1									
Thymoglobulin	ı									
administration	 	X			 		 		 	
Concomitant	ı									
medications	Х	X	Х	Х	X	Х	Х	Χ	Х	Х
Adverse Event	ı									
Monitoring	ı		X	Х	X	Х	Х	Х	Х	Х
Acute Rejection										
Assessment	1									

- (1) DVT exam will be done on day 0 and day1 (days Berinert vs.Placebo are given)
- (2) For scores indicating high risk for DVT, patient will have Doppler ultrasound.

*Day 4-7 assessments should be performed daily until the patient is discharged.

**If patient is discharged prior to day 7, day 7 lab assessments should be performed.

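### No coagulation panel is required between the second infusion on day 1 and the day 7 visit, and the day 1 draw is not timed against that infusion

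*Combined protocol and SAP*

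**What the plan says.** **Dosing.** The first dose is given before graft reperfusion and the second 24 hours after transplant; Appendix A allows day 1 ± 6 hours. Of these two doses, section 4.1.1 says "This will constitute the entirety of C1INH vs. placebo administration".

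**Coagulation schedule.** Section 4.6.3.2 asks for PT, PTT and INR before and after transplant on day 0. For days 1 to 7, section 4.6.3.3 lists "PT, PTT and INR (day 1 and day 7 only". Appendix A has a row for PT, PTT, D-dimer and fibrinogen, marked at screening, day 0, day 1 and day 7. Its day 7 column carries a window of ± 3 days; section 4.6.3.3 gives no window. The two lists differ in content: the text omits D-dimer and fibrinogen, and the appendix omits INR.

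**Timing on day 1.** The complement sample is tied to the dose: "C1 inhibitor, C3, C4 levels (prior to second dose of C1INH or placebo". The coagulation line in the same list carries no such words.

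**General statements.** Section 4.6.2.2 says "routine measurements of coagulation factors to evaluate DIC (D-Dimers, fibrinogen, PT, PTT) will be performed" and refers to Appendix A. Section 4.6.2.3 says that D-dimer and PT/PTT will be monitored, without times. Section 4.6.4.8 says "PT, PTT and INR tests will be performed per institutional SOC".

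**The concern.** Safety is the primary objective (section 2.1). Section 4.6.2.3 names the hazard itself: C1INH above normal baseline might induce coagulation abnormalities. Section 4.6.2.5 halts the study if any study-group patient shows coagulation abnormalities that suggest an impending thromboembolic event, and coagulation parameters are listed as a secondary safety endpoint. The earlier transplant experience that the plan cites as reassuring used 20 U/kg per dose. This trial gives 50 U/kg twice, about a day apart.

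If the laboratory schedule misses the days just after infusion 2, a comparison by arm may hold no value near the highest exposure. A normal result would then be weaker support for choosing a Phase III dose. Day 1 values could also come from either side of infusion 2 in different patients, so one labelled visit would mix two exposures.

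**Working it through.** **1. Which required draws must follow infusion 2?**

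| Source | Draw | Position relative to infusion 2 |
|---|---|---|
| 4.6.3.2 | Day 0, before and after transplant | Before |
| 4.6.3.3 and Appendix A | Day 1 | Not stated |
| Appendix A | Days 2 to 6 | None marked |
| 4.6.3.3 and Appendix A | Day 7 | After |
| 4.6.2.2 | Refers to Appendix A | Adds no draw |
| 4.6.2.3 | Monitored, no times | Adds no dated draw |
| 4.6.4.8 | Institutional standard of care | Adds no dated study draw |

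Two Appendix A footnotes matter. One asks for day 4-7 assessments daily until discharge. Even if that is read to include coagulation tests, they start on day 4. The other requires the day 7 laboratory tests after an early discharge but does not date them, so in that case a draw before day 4 is possible.

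**2. Length of the gap.** With infusion 2 on day 1 and the day 7 draw on days 4 to 10 (7 ± 3):

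- nominal: 7 − 1 = 6 days
- across the day 7 window: 4 − 1 = 3 to 10 − 1 = 9 days
- with the ± 6 hour infusion window added: 4 − 1.25 = 2.75 to 10 − 0.75 = 9.25 days

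The plan states no figure of its own for this gap.

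**3. Illustration of exposure.** The assumptions are one compartment, first-order decay, equal doses, a constant endogenous level, and half-life T = 2.5 or 3.8 days (section 4.1.1). This models added drug level, not coagulation effect. Peak means the added level just after infusion 2.

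The dose gap g comes from section 4.5.9 (first dose 60-120 minutes before reperfusion) and the day 1 window. Taking transplant time as reperfusion, g = 18 + 1 = 19 hours to 30 + 2 = 32 hours.

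*Just before infusion 2:* with r = 2^(−(g/24)/T), the share of peak is r/(1 + r).

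- T = 2.5: g = 19 gives 0.803/1.803 = 44.5%; g = 32 gives 0.691/1.691 = 40.9%
- T = 3.8: g = 19 gives 0.866/1.866 = 46.4%; g = 32 gives 0.784/1.784 = 43.9%

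A draw 12 hours before infusion 2 with g = 32 falls 20 hours after dose 1. The shares are 0.794/1.691 = 46.9% (T = 2.5) and 0.859/1.784 = 48.1% (T = 3.8). Section 4.1.1 also allows the first dose from admission; at an assumed g of 40 hours and T = 2.5 the share is 0.630/1.630 = 38.7%. So the range before infusion 2 is roughly 40-48%, and slightly lower if dose 1 is given early.

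*At h hours after infusion 2:* the share of peak is 2^(−(h/24)/T), whatever g is.

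| Time after infusion 2 | T = 2.5 | T = 3.8 |
|---|---|---|
| 12 h | 87.1% | 91.3% |
| 24 h (day 2) | 75.8% | 83.3% |
| 36 h | 66.0% | 76.1% |
| 3 days (day 4) | 43.5% | 57.9% |
| 6 days (day 7) | 18.9% | 33.5% |
| 9 days (day 10) | 8.2% | 19.4% |

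The 12 h and 36 h rows bound a day 2 draw when both 6-hour windows are used.

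**The case against.** The strongest reply is that patients are watched in other ways. Clinical assessment and adverse-event review are daily in the first week, and so is the hematology profile, with "measurements of WBC, RBC, platelets". Appendix A has a Wells row on days 0, 1 and 7, and section 4.6.2.2 requires assessment for thrombosis with each infusion, with Doppler for high scores. Appendix A also marks the complete physical examination daily, and section 4.6.4.1 says of it that "Wells Criteria Assessment will be done for presence of DVTs". Footnote (1), however, says "DVT exam will be done on day 0 and day1". All of this stands. A reader might infer that thrombosis goes unmonitored between infusion 2 and day 7, and the documents do not support that. What is missing is narrower: none of these measures PT, PTT, D-dimer or fibrinogen.

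A reader might also infer that the day 1 panel is always taken before infusion 2, or that no coagulation value will exist in the gap. Neither follows. The day 1 draw may happen to come after the dose, and institutional practice may add tests whose frequency the documents do not show. The point is only that nothing requires or labels such a value.

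Three further replies stand in part. Nothing in the documents shows that coagulation effects track peak drug level, so the percentages illustrate exposure and no more. Dosing ends with infusion 2, so a later value cannot change that patient's study treatment; its use is to inform the DSMB about later enrolees. And section 4.6.2.5 sets no laboratory threshold, so one more value would not by itself make the halting rule precise.

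**Conclusion.** The gap is real and limited. No coagulation panel is required to fall after infusion 2 until the day 7 visit. That is roughly 3 to 9 days later under the Appendix A window, and undated after an early discharge. The day 1 draw is not timed against infusion 2. A compliant site may therefore have no coagulation value near peak two-dose exposure, although such a value bears on a halting trigger and a safety endpoint.

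Under the one-compartment illustration, added C1INH is roughly 40-48% of peak before infusion 2, about 76-83% at 24 hours after it and about 19-33% at day 7. These figures rest on the plan's half-life and on the assumed equal doses and constant endogenous level. The gap itself rests only on the two schedules. It does not make the trial invalid or leave patients without safety monitoring. Closing it is a minor to moderate safety improvement.

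**What to change.** In section 4.6.3.3 and Appendix A:

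- keep the day 1 panel and label it as drawn before infusion 2;
- add one panel (PT, PTT, INR, D-dimer, fibrinogen) to the day 2 CBC/CMP draw, about 24 hours after infusion 2;
- use that same list of tests in both places;
- report the day 2 result by arm as change from a value drawn before dose 1, and send it to the DSMB.

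Moving the day 1 draw to after infusion 2 would save the extra panel but should not be done. Section 4.6.3.2 assures only PT, PTT and INR after transplant on day 0, and Appendix A has a single undivided day 0 mark. A day 1 draw before infusion 2 is thus the scheduled chance to see D-dimer and fibrinogen between the doses, while a result could still affect the second one.

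Cost: one laboratory panel per patient, 70 × 1 = 70 at most, at a blood draw that already takes place. Dosing, sample size and the listed endpoints do not change.

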4.6.3.4 Days 14 \pm 2 days & 28 \pm 2 days

- Concomitant medications
- Serum creatinine measurement
- Vital Signs

C1INH (Berinert®) IRI Study in Kidney Transplant

- CONFIDENTIAL
- Dialysis assessment
- Adverse Event Assessment
- Clinical Assessment
- Calculated Creatinine / Calculated GFR
- Hematology & chemistry profile

4.6.3.5 Days 60 ± 5 days & 90 ± 5 days

- Concomitant medications
- Serum creatinine measurement
- Dialysis assessment
- Vital Signs
- ACR assessment on Day 90
- Adverse Event Assessment
- Clinical Assessment
- Calculated Creatinine / Calculated GFR
- Hematology & chemistry profile

4.6.4 Observations And Measurements-see Appendix A.

4.6.4.1 Physical Examination

A complete physical examination will include; body weight and the examination of the following body systems: general appearance, skin, HEENT (head, ears, eyes, nose, throat), cardiovascular, pulmonary, abdomen, neurological, lymph nodes, spine and extremities (skeletal). In addition, Wells Criteria Assessment will be done for presence of DVTs.

4.6.4.2 Clinical Assessment

A clinical assessment will be preformed and will include a limited physical examination, the evaluation of the patient for clinical signs of infection, possible rejection, adverse events, and change in renal function. Any abnormalities will be recorded on the CRF.

4.6.4.3 Vital Signs

Vital signs; including blood pressure, heart and respiratory rate will be measured using clinically acceptable methods and devices at each clinic visit. Height will be measured at the screening visit only.

4.6.4.4 Serum Creatinine

Serum creatinine levels will be measured per institutional SOC.

4.6.4.5 Calculated Creatinine Clearance / Calculated GFR

Calculated creatinine clearance and GFR will be calculated using the MDRD or Cockroft & Gault formula.

4.6.4.6 Serum Creatinine Reduction Ratio

Serum creatinine reduction ratio will be calculated at 48 hours post transplant, using the formula described by Govani et al (2002).

4.6.4.7 Urine Output

Urine output will be collected and recorded for the first 5-7 days post-transplant.

4.6.4.8 PT, PTT and INR Tests

PT, PTT and INR tests will be performed per institutional SOC.

4.6.4.9 Hematology and Chemistry Profile

Hematology and Chemistry profile performed per institutional SOC and will include measurements of WBC, RBC, platelets, electrolytes, BUN, glucose, T Bili, Alb, Alk Phos, AST, ALT, BUN and Albumin.

4.6.4.10 ECG Testing

An ECG will be performed per institutional SOC.

4.6.4.11 ACR Assessment

An acute rejection assessment will be recorded on patients who were diagnosed with an ACR grade ≥ Grade 2 per the Banff grading system and received anti-rejection therapy.

4.6.4.12 Rate and Duration of Dialysis

Duration of dialysis will be measured by the number of sessions of dialysis treatment needed in the first 7 days post transplant. As for rate of dialysis, one dialysis session will represent the need for dialysis treatment.

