2.1 Study Objectives

In this study, we propose to investigate the application of preoperative and post-transplant doses of C1INH (Berinert®)vs. placebo in adult subjects receiving a deceased donor renal allograft considered at high-risk for IRI and DGF. We hypothesize that C1INH treated patients will demonstrate improved function of the kidney allograft compared to placebo, with equivalence in safety. We will also evaluate biopsies at transplant in all entered patients.

The primary objectives of this study are: Using a double blinded, placebo controlled format, we will:

- 1. Evaluate and compare the safety of C1INH (50 U/kg, round to the nearest 500unit) administered pre-transplant and 24 hrs post-transplant in recipients of kidney allografts from high risk deceased donors. The secondary objectives are to:
- 1. On the basis of safety and efficacy, determine appropriate Berinert® study dose for Phase III investigation, and
- 2. Determine appropriate endpoint choice for Phase III investigation.

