- Daily Calculated Creatinine Clearance for seven days post transplant or until discharge.
- Serum creatinine at 14, 28, 60, and 90 days post transplant.
- Total 24 hr urine output days 1-7 post-transplant.
- Rate of dialysis use at 14, 28, 60, and 90 days post transplant.

- Dialysis duration at 14, 28, 60, and 90 days post transplant.
- Rate of acute cellular and antibody mediated rejection episodes by day 90.
- Patient and graft survival by day 90.
- Calculated creatinine clearance at 14, 28, 60, and 90 days post transplant.
- Incidence of DGF as categorized by a DGF scale of increasing severity as follows:
- Grade 1 immediate urine production and no need for dialysis with creatinine reduction ratio (CRR) between time 0 of transplantation and day 7 post-transplantation >70%
- Grade 2 creatinine reduction ratio (CRR) between time 0 of transplantation and day 7 post-transplantation of >70% with need for dialysis
- Grade 3 creatinine reduction ratio (CRR) between time 0 of transplantation and day 7 post-transplantation <70% with no need for dialysis
- Grade 4 creatinine reduction ratio (CRR) between time 0 of transplantation and day 7 post-transplantation of <70% with need for dialysis.
- Protocol biopsies will be performed at the time of implantation.
 Pathological analysis will be done to determine if there is an increase in interstitial

CONFIDENTIAL	C1INH (Berinert®) IRI Study in Kidney Transplant
	fibrosis/tubular atrophy (IFTA), glomerulosclerosis, transplant glomerulopathy, and other markers of ischemic injury.
IMUNOSUPPRESSION REGIMEN	 Induction therapy using Thymoglobulin in divided doses for a total of 6mg/kg or Campath 1H 30mg SQ x 1. Calcineurin inhibition (Tacrolimus or Cyclosporine) will be delayed for minimum 24 hours post transplant. MMF will be started and used per standard of care (SOC). Corticosteroids will be used per SOC. Valgancyclovir will be used as the prophylaxis for CMV for a minimum of 6 months. Prophylaxis for bacterial and fungal infection will be per institutional SOC. Diagnosis and treatment of acute cellular or antibody-mediated rejection will be per institutional SOC.
STATISTICAL	Descriptive and comparative statistics
ANALYSIS	will be used to evaluate results
DURATION OF STUDY	90 days

3. Investigator(s) And Other Study Participants

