4.6 Study Variables

4.6.1 Efficacy Variables

4.6.1.1 Primary Efficacy Endpoints

For patients who do not require dialysis in the first 7 days:

- Proportion of patients enrolled with serum creatinine >3mg/dL on postoperative day 5.
- Proportion of patients with serum creatinine reduction ratio of < 30% from 24 to 48 hours post-transplant.

For patients who require dialysis in the first 7 days: (Excluding patients who get dialysis for hyperkalemia)

- The proportion of patients enrolled who require at least one session of dialysis in the first 7 days post transplant.
- Number of dialysis sessions per patient in the first 7 days post transplant.

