4.6.1.2 Secondary Efficacy Endpoints

- Daily serum creatinine for seven days post transplant or until discharge.
- Daily Calculated Creatinine Clearance for seven days post transplant or until discharge.
- Serum creatinine at 14, 28, 60, and 90 days post transplant.
- Total urine output in hours 16-24, 40-48 post transplant.
- Rate of dialysis use at 14, 28, 60, and 90 days post transplant.
- Dialysis duration at 14, 28, 60, and 90 days post transplant.
- Calculated creatinine clearance at 14, 28, 60, and 90 days post transplant.

CONFIDENTIAL

- Rate of acute cellular and antibody mediated rejection episodes by day 90.
- Patient and graft survival by day 90.
 - Protocol renal transplant biopsy at time of implantation.
 - Incidence of DGF as categorized by a DGF scale of increasing severity as follows:

Grade 1 - immediate urine production and no need for dialysis with creatinine reduction ratio (CRR) between time 0 of transplantation and day 7 post-transplantation >70%

Grade 2 - creatinine reduction ratio (CRR) between time 0 of transplantation and day 7 post-transplantation of >70% with need for dialysis

Grade 3 - creatinine reduction ratio (CRR) between time 0 of transplantation and day 7 post-transplantation <70% with no need for dialysis

Grade 4 - creatinine reduction ratio (CRR) between time 0 of transplantation and day 7 post-transplantation of <70% with need for dialysis

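### Dialysis duration at days 14, 28, 60 and 90 has no workable rule: the only definition counts sessions in the first 7 days

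*Combined protocol and SAP*

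**What the plan says.** - **Endpoint.** The Study Synopsis (2.2) lists "Dialysis duration at 14, 28, 60, and 90 days post transplant" among the secondary endpoints. Section 4.6.1.2 repeats it.
- **Measurement rule.** Section 4.6.4.12 states: "Duration of dialysis will be measured by the number of sessions of dialysis treatment needed in the first 7 days post transplant". It is the only rule for duration in the documents.
- **Rate of dialysis.** The same section continues: "As for rate of dialysis, one dialysis session will represent the need for dialysis treatment". No time window is attached. The matching endpoint in 4.6.1.2 is "Rate of dialysis use at 14, 28, 60, and 90 days post transplant".
- **Primary endpoint with nearly the same count.** Section 4.6.1.1 includes "Number of dialysis sessions per patient in the first 7 days post transplant". It stands under a lead-in that restricts it: "For patients who require dialysis in the first 7 days: (Excluding patients who get dialysis for hyperkalemia".
- **Data collection.** A "Dialysis assessment" is scheduled at days 14 and 28 (4.6.3.4) and again at days 60 and 90 (4.6.3.5).
- **Purpose.** One of the secondary objectives in 2.1 is to "Determine appropriate endpoint choice for Phase III investigation".

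Nothing elsewhere reconciles the rule with the endpoint. The copy reviewed shows no text under 6.1, and the synopsis entry on analysis promises only descriptive and comparative statistics.

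**The concern.** All four time points of the duration endpoint fall after the measurement window has closed. A duration that stops accumulating at day 7 cannot describe how long patients stayed on dialysis by day 14, still less by day 90. Someone free of dialysis by day 8 and someone dialysed throughout follow-up get the same four values if their first-week counts match. A patient first dialysed in the second week scores zero throughout.

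The trial is meant to inform the choice of a Phase III endpoint. If dialysis duration is among the candidates, it would be judged on numbers that carry nothing beyond day 7 and that, among patients dialysed in week 1, largely repeat a primary endpoint. That last step is an inference: section 2.1 does not name the candidates.

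**Working it through.** No planned figure has to be reproduced here, because neither sample size nor power enters. The check is to apply the stated rule at the stated times.

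**Step 1. Rule against time points.** The rule counts sessions with day ≤ 7. The endpoint is read at D = 14, 28, 60 and 90. Every D exceeds 7, so the count is the same at each D. The part of each period that the rule ignores is (D − 7)/D:

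| D | (D − 7)/D | Share ignored |
|---|---|---|
| 14 | 7/14 | 50% |
| 28 | 21/28 | 75% |
| 60 | 53/60 | 88% |
| 90 | 83/90 | 92% |

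These shares describe the rule. They are not effect estimates.

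**Step 2. Three invented patients.** The session days are assumptions chosen to show how the rule works.

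| Patient | Session days | Rule as written, D = 14/28/60/90 | Cumulative sessions to D |
|---|---|---|---|
| A | 1, 3 | 2/2/2/2 | 2/2/2/2 |
| B | 1, 3, 5, then alternate days from 8 to 28 | 3/3/3/3 | 7/14/14/14 |
| C | 10, 12, 14, 17, 19, 21 | 0/0/0/0 | 3/6/6/6 |

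For B, four sessions fall on days 8 to 14 (3 + 4 = 7) and eleven on days 8 to 28 (3 + 11 = 14). The rule is right only for A, whose dialysis ended within the first week. It misses 11 of B's 14 sessions and all 6 of C's.

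**Step 3. The other reading.** Suppose 4.6.4.12 was written only for the primary session count in 4.6.1.1, whose wording it resembles. The day 14 to 90 endpoint then has no rule: the documents do not say whether duration means sessions or days, or where counting starts and ends.

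**Step 4. Overlap with the primary endpoint.** The two counts differ in one respect. The primary count applies to patients dialysed in week 1 and leaves out those dialysed for hyperkalemia, while 4.6.4.12 says nothing about hyperkalemia.

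**Step 5. What still captures later dialysis.** The 7-day limit is attached to duration only. The rate rule has no such limit, and dialysis is assessed at all four later visits.

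**The case against.** The strongest reply is that 4.6.4.12 may never have been meant for the later time points. Its unit and window follow the fourth primary endpoint closely, so it may be wrong to say that four values collapse into one. This stands as a caution about which reading is right. It does not rescue the endpoint, which on that reading has no definition. The section title pairs rate with duration, the same two terms that the secondary endpoints use, so a reader would naturally take it as their definition.

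The second reply is that little is lost. Rate of dialysis use at the same four days already separates a patient off dialysis early from one still dialysed late. This also stands, and it limits the consequence: what is missing is the amount of dialysis, not the fact of it.

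Three stronger readings are tempting, and the documents do not support them:

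- **That dialysis after day 7 goes unobserved.** The visit schedule and the rate endpoint show otherwise.
- **That a number of misclassified patients can be derived from the planning rates of delayed graft function.** Those rates do not say how often dialysis continues or starts after day 7, nor how dialysis for hyperkalemia was treated.
- **That antibody-mediated rejection is not recorded because 4.6.4.11 is limited to treated acute cellular rejection of Banff grade 2 or higher.** Both types are diagnosed under institutional practice, and the clinical assessment and adverse event records can capture them. Appendix A has a row for acute rejection in general, but its columns after Day 14 are not visible. The case report form is not available either.

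**Conclusion.** The inconsistency is real and worth correcting. Under the literal reading, one value per patient is repeated four times and post-day-7 sessions count for nothing. Under the narrower reading, the endpoint lacks a unit and a window. The conclusion rests only on the wording of 4.6.4.12 set against 2.2 and 4.6.1.2, and needs no assumption about event rates.

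The reach is one secondary efficacy endpoint. Power and the primary comparison are untouched. No bias or misclassification count can be given, because the documents report no dialysis rate after day 7.

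A separate note of low weight concerns rejection. The visible recording rule (4.6.4.11) is narrower in type, grade and treatment than the rejection endpoint in the synopsis, in 4.6.1.2 and in the secondary safety list, which covers cellular and antibody-mediated episodes without such limits. The two should agree, but material not visible here may already settle it.

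**What to change.** **In 4.6.4.12:**

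- Limit the 7-day window to the primary session count.
- Define dialysis duration at day D (14, 28, 60, 90) as the cumulative number of sessions from transplant to D. This keeps the protocol's own unit. Days from transplant to the last session would be a poorer choice: one isolated session on day 60 would score 60, and a session on day 0 would score the same as none.
- Close the count at calendar day D, since the visits carry windows of ±2 or ±5 days (4.6.3.4, 4.6.3.5).
- Record first and last session dates, and whether dialysis is ongoing, at the dialysis assessments already scheduled.
- Report death and graft loss before D separately, so that a count cut short is not read as a good result.
- State whether the hyperkalemia exclusion applies to this endpoint.

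**For rejection (4.6.4.11 and 4.6.3.5):** count all cellular and antibody-mediated episodes diagnosed by day 90 under institutional practice, and report treated cellular rejection of grade 2 or higher as a subset. If the case report form or the later columns of Appendix A already do this, only the wording needs aligning.

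**Cost:** protocol wording, a few case report form fields, and some effort to obtain session records from outside dialysis units. No visit, test or biopsy is added.
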